18.4. Handling of Missing Data, Dose Adjustments, and Early Withdrawals

For the efficacy analyses, subjects who do not have a TOC assessment will be assigned as treatment failures. For subjects who withdraw from the study early, every effort will be made to collect TOC visit information at the point of withdrawal.

18.5. Prior and Concomitant Medications

Prior and concomitant medications will be coded using the World Health Organization Drug Dictionary terminology. The number and percentage of subjects taking each medication before and after the first dose of study drug will be tabulated by treatment group. Medications taken and stopped prior to the first dose of study drug will be considered prior medications. Medications

started on or before the FU visit date with missing start dates or stop dates after the first dose of study drug will be considered concomitant medications.

18.6. Efficacy

18.6.1. Efficacy Assessments

Efficacy assessments will be based on VSS scores, clinical evaluations, QOL outcomes, mycological testing, and additional antifungal use by the TOC visit and FU visits.

18.6.1.1. The following treatment outcome definitions will be used for the assessment of efficacy relative to baseline: Clinical Outcome

- Clinical Cure: Complete resolution of signs and symptoms with total composite score of 0 on the VSS Scale and with no additional antifungal therapy required based on investigator's judgment
- Clinical Improvement: partial resolution of signs and symptoms with total composite score of 1 or 2 on the VSS Scale and with no additional antifungal therapy required based on investigator's judgement.
- Clinical Success: at least 50% reduction from Baseline in the total composite VSS score with no additional antifungal therapy required based on investigator's judgment
- Clinical Failure: Persistence and/or worsening of signs and symptoms or need for additional antifungal therapy

18.6.1.2. Mycological Outcome

- Mycological Eradication: negative culture for growth of *Candida* species
- Presumed Eradication: Subject is asymptomatic, therefore cultures not done
- Mycological Persistence: positive culture for growth of *Candida* species

18.6.2. Efficacy Analyses

The efficacy analyses will be conducted using the MITT (primary analysis population), ITT and PP populations to evaluate ibrexafungerp.

The primary efficacy endpoint, the percentage of subjects with Clinical Cure at TOC will be assessed on the MITT population and will present the Clinical Success rate and the 95% confidence interval calculated using the method of Clopper and Pearson. All other efficacy data will be summarized, but not subject to formal statistical analysis.

18.7. Safety

18.7.1. Safety Assessments

Safety will be evaluated throughout the study, including the following parameters: AEs, treatment discontinuations, physical examination, vital signs, safety laboratory tests, and prior and concomitant medications.

AEs will be recorded and reviewed at all scheduled and unscheduled study visits from the time the Informed Consent Form is signed. An abbreviated physical examination, including general appearance and an overall examination of body systems, will be conducted at Screening, at the TOC visit and at the first FU (14 Days after EOT) visit. Vital signs, including blood pressure (systolic and diastolic), heart rate, respiratory rate and body temperature will be measured at the Screening and TOC visits and at unscheduled visits, if needed. Safety laboratory test (hematology and blood chemistry) will be measured at Screening, at the TOC visits and at unscheduled visits, if needed. All prior and concomitant medications taken before Screening through the TOC visit will be recorded. Only the use of antifungal medications, vaginal (topical) medications, antibiotics for any reason or any other medications to treat an AE will be recorded after the TOC visit through the last study visit.

Study procedures are described in [Section 14.0](#) and safety assessments and monitoring are described in [Section 16.0](#).

18.7.2. Safety Analyses

Safety analyses will be conducted using the safety population.

AEs will be coded using the Medical Dictionary for Regulatory Activities (MedDRA) Version 19.1 or higher. The incidence and severity of treatment-emergent AEs and SAEs and their relationship to treatment will be summarized by system organ class and preferred term. The percentage of subjects who discontinued study treatment and the reasons for discontinuation will be summarized by treatment group.

Safety laboratory evaluations and vital signs will be summarized as observed values and as changes from Baseline. In addition, shifts (with respect to the reference range) from Baseline will be presented by treatment group for laboratory tests.

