10.4. Number of Centers

Multiple centers will participate in subject enrollment and treatment.

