14.7. Safety Laboratory Tests

Safety laboratory tests will be performed by a qualified local laboratory. Samples for safety laboratory tests will be collected at the Screening, TOC, and at any unscheduled visit, if needed. If indicated, these may be done more frequently as follow up to a laboratory abnormality.

The following laboratory parameters will be determined:

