14.7.2. Blood Chemistry

- Glucose
- Albumin
- Sodium
- Potassium
- Alkaline Phosphatase
- Creatinine
- Total creatine phosphokinase (CPK)
- Aspartate aminotransferase (AST/SGOT)
- Alanine aminotransferase (ALT/SGPT)
- Gamma glutamyl transferase (GGT)
- Bilirubin (total, direct and indirect)
- Total protein

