16.7. Grading of Adverse Events

The severity (or intensity) of an AE refers to the extent to which it affects the subject's daily activities and will be classified by the investigator as mild, moderate or severe using the following criteria:

- Mild: Awareness of sign or symptom, but easily tolerated. Not likely to require medical attention.
- Moderate: Discomfort enough to cause some interference with daily activity. May require medical intervention.
- Severe: Intense enough to disrupt daily activities. Likely requires medical intervention.

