6.6.2. Clinical Laboratory Assessments

Laboratory data will be presented as per the international system of units, universally abbreviated as SI (from the French ‘system international’).

Hematology and blood chemistry will be summarized using descriptive statistics by treatment group and visit. Change from baseline values will be summarized similarly by treatment group for each post-baseline scheduled visit. Number and percentage of subjects with urine pregnancy test will be provided by treatment group and visit.

Shift tables from baseline to post-baseline for hematology and blood chemistry assessment, describing shifts to abnormality (low, normal, or high), will be provided. The number of subjects with a non-missing result at both baseline and a specific post-baseline scheduled visit will be used as denominator for that post-baseline scheduled visit.

Separate listings of all hematology, blood chemistry and urine pregnancy data will be provided. In addition, separate listings for hematology, blood chemistry, and urine pregnancy data will be provided for each parameter where a subject had at least one abnormal result.

All laboratory tests required at screening and/or baseline only will be listed.

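### Enzymes and bilirubin from local laboratories are not scaled to the local upper limit of normal and are shifted only as low, normal or high, so no described analysis gives the rate of marked elevation by regimen

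*Protocol*

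**What the plan says.** Protocol 14.7 states: "Safety laboratory tests will be performed by a qualified local laboratory". Protocol 10.4 adds: "Multiple centers will participate in subject enrollment and treatment". The chemistry panel in 14.7.2 includes ALT, AST, GGT, alkaline phosphatase, CPK and bilirubin. Protocol 14.7 and Table 1 schedule these tests at Screening and at the test-of-cure (TOC) visit, with others only if needed.

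For the analysis, Protocol 18.7.2 plans two displays. The first is continuous: "Safety laboratory evaluations and vital signs will be summarized as observed values and as changes from Baseline". The second is categorical: "In addition, shifts (with respect to the reference range) from Baseline will be presented by treatment group for laboratory tests". SAP 6.6.2 fixes the units ("Laboratory data will be presented as per the international system of units, universally abbreviated as SI") and limits the shift tables to three states, "describing shifts to abnormality (low, normal, or high), will be provided". It also plans listings of all results and separate listings for each parameter with any abnormal result. SAP 6.1 includes the minimum and maximum among the descriptive statistics, and SAP 6.7 plans a profile for every subject.

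SAP 6.1.1 recalculates the laboratory baseline for Cycle 2 and falls back on the last Cycle 1 value when no new one exists.

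**The concern.** Safety and tolerability form a secondary objective (Protocol 8.2). The two Phase 3 trials described in Protocol 7.1.4 gave one day of treatment. Here Group B receives three or seven days, and Cycle 2 allows up to 14. A reader of the report will want to know how many subjects on each regimen had a marked rise in transaminases, with or without a rise in bilirubin.

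The planned tables are poorly suited to that question, for three reasons.

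- Putting results in common units does not put them on a common reference limit, so pooled values from different laboratories do not measure the same degree of abnormality.
- The *high* state begins just above the ULN and has no upper bound, so slight and large rises look the same.
- For a given analyte, a subject who starts high has no higher state to move to. Group B admits diabetes, HIV, debilitation and immunosuppressive therapy, and Protocol Appendix 1 allows tacrolimus, cyclosporine and amiodarone with monitoring. High baselines are therefore admissible, although the documents give no figure for how common they are.

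**Working it through.** The plan states no figure to reproduce here: there is no formal sample size calculation and no laboratory threshold. The check applies the plan's own display rules to an example. The only input taken from the documents is about 50 subjects per duration (Protocol 18.1, SAP 5.4). The enzyme values are illustrative. The documents give no ULN, so a local ALT ULN of 30 to 55 U/L is assumed. Changing the unit multiplies every value by the same constant, so it does not affect the multiples below.

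**1. Shift table.** The rule is: high if the value exceeds 1 x ULN. A baseline of 1.2 x ULN is high, and a TOC value of 9 x ULN is high. The cell is high to high, although the rise is 9/1.2 = 7.5-fold. From the same baseline, TOC values of 1.01, 3, 5, 9 and 20 x ULN all fall in that one cell.

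**2. Mean change.** One such subject contributes (9 - 1.2)/50 = 7.8/50 = 0.156 x ULN to the mean of a 50-subject arm. That is 0.156 x 30 = 4.7 U/L to 0.156 x 55 = 8.6 U/L. The mean would hardly show it.

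**3. Maximum change.** The same subject's change is 7.8 x 30 = 234 U/L to 7.8 x 55 = 429 U/L. The planned maximum would show a value of this size, but a maximum is not a count.

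**4. Pooling across laboratories.** A result of 120 U/L is 120/30 = 4.0 x ULN at one end of the assumed range and 120/55 = 2.2 x ULN at the other. The order can reverse: 110 U/L where the ULN is 35 is 110/35 = 3.1 x ULN, which is more abnormal than 120 U/L where the ULN is 55. The largest value in U/L need not be the largest multiple.

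**5. Cycle 2.** Protocol section 15 starts Cycle 2 at the Baseline visit, and Table 1 schedules no safety laboratory test there. Unless an extra sample is taken, SAP 6.1.1 makes the last Cycle 1 value the new baseline. For a subject who attended TOC, that value was taken after treatment. Suppose a subject is normal at Screening, at 1.2 x ULN at the Cycle 1 TOC and at 9 x ULN at the Cycle 2 TOC. Cycle 1 shows normal to high and Cycle 2 shows high to high. No display compares the Cycle 2 value with the pre-treatment state.

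**6. With ULN categories.** Using <=1, >1-3, >3-5, >5-8 and >8 x ULN, the example in step 1 moves from >1-3 to >8. In step 5, the Cycle 2 value set against the pre-treatment baseline moves from <=1 to >8.

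**The case against.** The case for leaving the plan alone has real content.

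- **Individual rises are not lost.** Change from baseline with its maximum, abnormal-result listings and subject profiles are all planned. A reader might infer that results are left in unharmonised units, or that three-state shifts are the only output. Neither is so: the SAP requires SI units and keeps the continuous summaries. What is missing is scaling to local ULN and a tabulated rate.
- **A high baseline blocks only one analyte.** A reader might infer that such a subject cannot register any upward shift. Shift tables are per parameter, so a subject with a high GGT can still shift in ALT, AST, CPK or bilirubin. Exclusion 9 in Protocol 11.2 also removes some subjects with laboratory abnormalities.
- **The severity scale does not force a large rise into the lowest grade.** Protocol 16.7 ties severity to daily activities, so a reader might infer that any symptom-free rise, however large, counts as mild. The definition reads: "Mild: Awareness of sign or symptom, but easily tolerated. Not likely to require medical attention". Its second sentence makes that grading contestable for a rise such as 9 x ULN. The adverse event tables still do not supply the missing count: Protocol 16.1 makes a laboratory abnormality an adverse event only if the investigator judges it clinically significant, and sets no numeric threshold.
- **There is longer prior exposure.** Protocol 7.1.4 reports up to 800 mg/day for 28 days in Phase 1, against 600 mg/day here, and more than 1500 people exposed. Protocol 16.3 no longer defines events of clinical interest, and the revision history explains that the safety profile is well established. This lowers the expected yield. But that change removed site reporting of such events; it does not argue against tabulating data already collected.
- **Few events are likely,** with about 50 subjects per regimen and usually one post-baseline sample per cycle. This stands, and it limits what the tables can show.
- **The table shells are in a separate document** (SAP section 3) that was not available, so the point is confined to what the protocol and SAP describe.

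**Conclusion.** The point holds as a gap in how laboratory safety is summarised. Values are not scaled to local ULN, and three-state shifts cannot separate a slight rise from a large one or show an upward move from a high baseline in the same analyte. The Cycle 2 baseline rule can create that situation even in subjects who were normal before treatment. No analysis described in the protocol or SAP gives the rate of marked elevation by regimen.

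The size is modest. No sample is missing, individual values can be traced, and the primary endpoint is unaffected. The high-to-high result follows from the plan's rules alone. The U/L figures rest on the assumed ULN range of 30 to 55. The number of subjects with a high baseline cannot be estimated from the documents. The change is worth making because safety is a stated objective and the cost is low.

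**What to change.** In SAP 6.6.2 and Protocol 18.7.2:

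1. Express ALT, AST, GGT, alkaline phosphatase, CPK and bilirubin as multiples of the local ULN before summarising.
2. For ALT and AST, tabulate baseline against worst post-baseline category (<=1, >1-3, >3-5, >5-8, >8 x ULN) by regimen and by cycle. Show Cycle 2 also against the original pre-treatment baseline.
3. Add a count, by regimen and cycle, of subjects with ALT or AST >3 x ULN together with total bilirubin >2 x ULN.

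The cost is a few extra table shells and no new samples. One thing needs confirming: a three-state shift table can be built from flags alone, and Protocol 17.3 places laboratory normal values in the site files. The sponsor should therefore check before database lock that numeric local ULNs are in the database. With about 50 subjects per regimen many cells will be empty, so the tables should be read as descriptive.

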19. ETHICS AND PROTECTION OF HUMAN PATIENTS

19.1. Ethical Conduct of the Study

The study will be conducted in accordance with the protocol, the ethical principles established by the Declaration of Helsinki (as amended in Fortaleza, Brazil, October 2013), the International Conference on Harmonisation (ICH) Good Clinical Practice (GCP) Guidelines, the US Code of Federal Regulations (CFR) sections that address clinical research studies, applicable European Union regulations and/or other national and local ethical and legal requirements, as applicable.

19.2. Institutional Review Board/Ethics Committee Review

The PI or Sponsor/CRO must provide the IRB/EC with all appropriate materials, including a copy of the subject ICF. The study will not be initiated until the PI or CRO obtains written approval of the protocol and the subject ICF from the appropriate IRB/EC, and copies of these documents are received by the Sponsor. Appropriate reports on the progress of this study will be made by the PI to the IRB/EC, medical monitor, and Sponsor in accordance with applicable government regulations and in agreement with policy established by the Sponsor.

19.3. Informed Consent

The ICH issued guidelines to provide protection for human subjects in clinical investigations. The ICH Tripartite Guideline for Good Clinical Practice establishes the general requirements for informed consent. Each subject will be provided with oral and written information in a language they can understand that describes the nature and duration of the study. Before undergoing screening, each subject must consent in writing to study participation. The patient will sign and personally date the subject ICF. The person rendering consent will also sign and personally date the subject ICF as the person who obtained the consent of the subject. The original signed subject ICF will be retained with the study center's records. Each subject will receive a copy of her signed subject ICF. In addition, the PI, or his or her designee, must document in the case history that informed consent was obtained before study participation.

19.4. Future Use of Samples

Biological samples collected during the study, including *Candida* spp. isolates (see Section 14.9 and Section 14.10), may be maintained in repositories for potential future use. Future research of *Candida* isolates may include *in vitro* susceptibility testing of new or existing antifungals or analysis of mechanisms of resistance. All samples will be identified only by a coded number to maintain subject confidentiality.

19.5. Subject Privacy and Subject Confidentiality

All laboratory specimens, evaluation forms, reports, and other records that leave the site will be identified only by a coded number to maintain subject privacy and confidentiality. All records will be kept in a locked file cabinet. All computer entry and networking programs will be performed with coded numbers only. Clinical information will not be released without written permission of the subject, except as necessary for monitoring by the medical monitor, IRB/EC, the Food and Drug Administration (FDA), the Sponsor or where required by law. All local privacy laws must be followed.

19.6. Study Termination

The PI, the sponsor, the FDA, and the IRB/EC each reserve the right to terminate the study in the interest of subjects' safety and welfare. The sponsor reserves the right to terminate the study at any time for administrative reasons. The sponsor also reserves the right to discontinue study enrolment if a particular cohort is proving difficult to enroll.

19.7. Financial Disclosure

The financial interests of all investigators from all participating clinical centers must be collected prior to study initiation and 1 year following the completion of the clinical trial.

21. APPENDICES

APPENDIX 1. PROHIBITED MEDICATIONS AND MEDICATIONS TO BE ADMINISTERED WITH CAUTION

Prohibited Medications

The use of any topical vaginal corticoids and topical vaginal contraceptives is prohibited during the study. No systemic or topical vaginal antifungal treatment other than the study drug is allowed during the study unless used as rescue medication after the subject has been documented as not responding to study drug. No investigational drugs other than the study drug are allowed within 30 days before Screening and for the entire duration of the study. In addition, the medications listed below are also prohibited.

Strong CYP3A4/5 inhibitors and CYP3A4/5 inducers

CYP	Strong Inhibitors ^a	Inducers ^a
3A4/5	Ketoconazole Itraconazole	bosentan carbamazepine phenytoin rifampin St. John's wort long-lasting barbiturates efavirenz etravirine

^a. The CYP3A4/5 inhibitors and CYP3A4/5 inducers listed in this table are not permitted during the 7 days prior to enrollment and during study treatment until TOC.

Medications to be administered with Caution and Monitored as Appropriate

CYP3A4 substrates

CYP	Substrates
3A4	
In vitro, ibrexafungerp (SCY-078) was an inhibitor of CYP3A mediated metabolism of midazolam, but was only a weak inhibitor of metabolism of testosterone. The clinical significance of this inhibition is unknown; caution should be exercised when administering ibrexafungerp (SCY-078) with drugs known to be CYP3A sensitive substrates with narrow therapeutic index, such as midazolam and cyclosporine.
 
Subjects receiving sirolimus, tacrolimus, warfarin, cyclosporine or amiodarone are permitted for enrollment in the study and these medications may be administered concomitantly with ibrexafungerp (SCY-078) with close monitoring. Dosing adjustments and subsequent monitoring of sirolimus and warfarin should be undertaken in accordance with product prescribing information for the respective agents.

OATP1B3 substrates

OATP	Substrate
1B3	
In vitro, ibrexafungerp (SCY-078) is an inhibitor of the OATP1B3 liver uptake transporter. The clinical significance of this inhibition is unknown; however, there is a potential risk for increased exposure of the concomitant medications (arising from lowered hepatic clearance) when administering ibrexafungerp (SCY-078) with drugs known to be OATP1B3 selective substrates. Therefore, caution should be exercised when administering ibrexafungerp (SCY-078) with drugs known to be OATP1B3 selective substrates such as telmisartan, including monitoring the subject for signs of overexposure associated with the concomitant medications as described in the product prescribing information.

P-gp Drug Substrates

digoxin, colchicine, dabigatran

Sources:

- FDA Draft Guidance for Industry. Drug Interaction Studies – Study Design, Data Analysis, and Implications for Dosing and Labeling. 2012.
- Drug interactions in infectious disease by Stephen C. Piscitelli, Keith Rodvold (2007)
- UCSF-FDA Transportal

APPENDIX 2. VULVOVAGINAL SIGNS AND SYMPTOMS SCALE

SIGNS:

To be rated by the investigator during the vulvovaginal examination

Sign	Absent 0	Mild 1	Moderate 2	Severe 3
Edema				
Erythema				
Excoriation or fissures				

- Definitions: Absent: none Mild: slight
- Moderate: definitely noticeable Severe: marked, intense

SYMPTOMS:

To be rated by the subject

Symptom	Absent 0	Mild 1	Moderate 2	Severe 3
Burning				
Itching				
Irritation				

Definitions:

- Absent: I have no discomfort (i.e., burning, itching, irritation)
- Mild: I have some discomfort (i.e., burning, itching, irritation), but it does not bother me much
- Moderate: I have discomfort (i.e., burning, itching, irritation), which is annoying, but not enough to affect what I am doing
- Severe: I have discomfort (i.e., burning, itching, irritation), which is annoying enough to affect what I am doing

